Screening Population (n=100) Willing, consented adults (≥ 21 years) Informed consent Pre-Registration (n=up to 100) Screening Physical exam, medical/surgical history, baseline symptoms, concomitant medications, alcohol and tobacco use assessment Laboratory studies and research blood draw Stool antigen test for Helicobacter pylori Esophagogastroduodenoscopy (EGD) with research biopsies **Study Population** Histologically-confirmed gastric intestinal metaplasia (GIM) and/or multifocal atrophic gastritis (MAG) Helicobacter pylori negative Registration/Randomization (n=50) V Meriva® (n=25) Placebo (n=25) 500 mg capsule twice daily 1 capsule twice daily Intervention Length = 6 months Weekly (+/- 2 days) phone calls to assess compliance Return visit at 3 months (+/- 7 days) for adverse event and concomitant medication(s) assessment, blood tests for safety and toxicity, collect unused study agent, and dispense new supply of study agent.

Post-intervention Evaluation (n=44)

- Month 6 +/- 14 days or early termination
- Physical exam, AE/concomitant medication, and alcohol/tobacco use assessments
- Was it Worth It (WIWI) Questionnaire
- Repeat laboratory studies and research blood draw
- EGD with research biopsies and path review

Follow Up

 Phone call at Month 7 (+/- 14 days) or 30 days (+/- 14 days) after the Post-Intervention Evaluation (in the event of early termination) to assess AEs and concomitant medications

Endpoints

- Primary: To compare the absolute change in Interleukin-1beta (IL-1β) cytokine levels (measured by Luminex Assay) in the gastric mucosa from baseline to 6 months among participants randomly assigned to receive either Meriva-500® or placebo
- Secondary Endpoints (prioritized order):
 - O Safety: To determine the safety and tolerability of Meriva® versus placebo
 - Change in Histology Gastric Score (HGS) from baseline to 6 months for Meriva® versus placebo
 - In participants with precancerous gastric lesions, to determine the effect of Meriva® versus placebo on the following endpoints (comparing the change from baseline to 6 months):
 - Additional gastric mucosal cytokine/chemokine levels (interleukin 9 [IL-8], tumor necrosis factor alpha [TNFα], and inducible protein 10 [IP-10] quantified by Luminex Assay);
 - Gastric mucosal DNA damage, as assessed by immunohistochemistry (IHC), of the biomarkers 8-hydroxy-2' –deoxyguanosine (8-OHdG) and phosphorylated subtype of histone H2A [H2AX];
 - Associations between proinflammatory cytokine genotype status (IL-1β, IL-8, and TNFα single nucleotide polymorphisms [SNPs] characterized at baseline) and the above outcomes. These will be considered exploratory analyses.

TABLE OF CONTENTS

Cover page	
Investigators	2
Contacts	4
Schema	5
1. Objectives	
1.1 Primary objective	10

1. OBJECTIVES

1.1 Primary Objective

To compare the change in gastric mucosal Interleukin 1beta (IL-1 β) cytokine level, quantified by Luminex assay technology, after a 6 month intervention in participants randomly assigned to the Meriva® (curcuminoids) versus placebo arms.

1.2 Secondary Objectives

After a 6-month intervention in participants randomly assigned to the Meriva® versus placebo arms:

- To determine the safety and tolerability of Meriva® versus placebo;
- To compare changes in Histology Gastric Score (HGS) from baseline to 6 months for Meriva® versus placebo;
- To compare changes in additional gastric mucosal cytokine/chemokine levels (Interleukin 8 [IL-8], tumor necrosis factor alpha [TNFα], and inducible protein 10 [IP-10]; quantified by Luminex assay);
- To compare changes in gastric mucosal DNA damage as assessed by Immunohistochemistry (IHC), of the biomarkers 8-hydroxy-2' –deoxyguanosine (8-OHdG) and phosphorylated subtype of histone H2A (H2AX);
- To explore associations between proinflammatory cytokine genotype status (IL-1 β , IL-8, and TNF α single nucleotide polymorphisms [SNPs]; characterized at baseline) and the above outcomes.

2. BACKGROUND

2.1 Gastric Cancer

Global Burden: Gastric cancer (GC) is the 4th most common incident cancer and the 2nd leading cause of cancer death worldwide.¹ Approximately 990,000 people are diagnosed with GC worldwide, of whom close to 75% die from this disease.² GC also is responsible for one of the highest cancer burdens, as determined by disability-adjusted life years lost.³ Despite the overall decrease in the incidence of GC since the 1930s, the annual global burden of cancer is projected to double by 2030 to 22.2 million incident cases and 13.1 million deaths, with over two-thirds of the burden in resource-limited nations.^{4,5} In the US, the American Cancer Society estimates that in 2015 24,590 new cases of GC will be diagnosed and approximately 10,720 individuals will die from this type of cancer.⁶ The average risk that a person will develop GC in his/her lifetime is about 1 in 111, with the risk being 2 to 3-fold higher in men than women. However, GC incidence rates vary dramatically across different countries and are higher in less developed countries.² GC is more common in East Asia, Southern and Eastern Europe, and South and Central America whereas the lowest incidence rates are observed in Africa and North America.⁷ Although nearly 60% of the new GC cases are diagnosed in Asia,⁸ significantly better outcomes

have been reported among Asian individuals compared to those diagnosed in Western countries.⁹ Five-year GC survival rates are 40% lower in the US and Europe compared to Japan.¹⁰

Risk Factors. The risk factors for the development of gastric cancer include: male sex, older age, *Helicobacter pylori* status, tobacco smoking, diet, living in places with high altitude, low socioeconomic status, and being part of the Asian, Hispanic, and African American communities. 11, 12

Racial/ethnic GC Disparities. Although the number of deaths from GC has been steadily declining, significant geographical and racial/ethnic health disparities in GC incidence and mortality continue to be observed. The observed decline in GC incidence has been occurring more in tumors of the non-cardia, which are mostly attributable to *H. pylori*, smoking, and high salt diets. Asians, Hispanics and Blacks in the U.S. have been reported to have a higher proportion of distal GC (tumors in the body, antrum, and pylorus) compared to Whites, which are most commonly diagnosed with proximal GC (tumors in the cardia and fundus). A significantly higher incidence of GC has been observed among Asians, followed by Blacks and Hispanics compared to Whites. It, 15, 16 Interestingly, GC incidence is similar in all racial/ethnic groups in the U.S. until age 60–64, where Asian incidence rates increase dramatically. From 1992 to 2009, overall 3-year survival was highest among Asians (26%), followed by Blacks, Hispanics, and Whites, which had comparable survival rates (~19%). Geographical differences in the incidence of GC have also been observed among regions in the U.S., with the highest incidence reported in the West followed by the Northeast.

The reasons for the geographic and racial/ethnic GC disparities remain incompletely understood and may be due to a combination of factors which may include barriers to healthcare, environmental factors, and/or genetic factors.¹⁷ Latin America has a significant GC burden, with a concentration of disease in the mountainous regions of the Pacific littoral zone, where the mortality-to-incidence ratio is extremely high at 0.82. In the U.S., GC represents a marked health disparity where non-whites, including Hispanics, have nearly 2-fold higher incidence rates, for reasons that remain largely uninvestigated. Hispanics are projected to comprise 25% of the U.S. population by 2040-2050, and represent a large at-risk population, particularly immigrants from high incidence areas, such as Central America. However, when evaluating cancer susceptibility factors in the U.S., Hispanics from different populations are usually grouped together.

A comprehensive understanding of the factors affecting GC disparities will help to target educational programs to individuals at higher risk of GC and to develop prevention strategies, including chemoprevention, to reduce the disease burden across all racial/ethnic groups.

2.2 Meriva®/curcuminoids

Curcumin is a phenolic antioxidant compound derived from the rhizome of the plant *Curcuma longa*. Curcumin has long been used as a spice in India and other parts of Asia and is considered a safe food additive. This bioflavonoid is a potent inhibitor of arachidonic acid metabolism, and blocks both lipoxygenase and cyclooxygenase activity in the intestinal mucosa. Curcumin exerts a variety of additional immunomodulatory and antioxidant effects and is thought to have broad chemopreventive potential through a variety of molecular mechanisms and cellular pathways, as recently reviewed.²¹

Meriva® is a unique curcumin product available to the investigative team by Thorne Research (Dover, ID). The overall curcuminoid absorption from the Meriva® formulation is about 29-fold higher than that of the corresponding unformulated curcuminoid mixture. The improved absorption and enhanced plasma curcuminoid profile make Meriva® an attractive candidate agent for chemoprevention trials.

2.3 Rationale

Gastric intestinal metaplasia and chemoprevention: Gastric precancerous lesions, such as gastric intestinal metaplasia (GIM) are prevalent both in high and low incidence regions of the world. GIM is the replacement of gastric mucosa by an epithelium that histologically resembles intestinal mucosa and is a key event in gastric carcinogenesis. The prevalence of GIM varies depending on the rate of *H. pylori* infections in the population.²³ Intestinal metaplasia is present in approximately 20% of all gastric biopsies,²⁴ but up to 10% of patients with GIM will progress to GC.²⁵ Current guidelines for symptomatic individuals with extensive GIM recommend endoscopic surveillance every 3 years.²⁶ Unfortunately, the limited efficacy of *H. pylori* eradication strategies in patients with GIM emphasizes the need for other pharmacologic intervention to prevent GC progression.^{27, 28} *H. pylori* induced chronic gastritis increases the level of COX-2 expression in the stomach mucosa. Enhanced expression of COX-2 is also observed in intestinal metaplasia and dysplasia.²⁹ NSAID and aspirin use have been examined as GC chemoprevention agents. Use of these agents has been associated with a reduction in the odds of distal gastric cancer.^{30, 31}

Curcumin is a phenolic antioxidant compound derived from the plant *Curcuma longa* that is used as a spice in India and has been shown to block both lipoxygenase and cyclooxygenase activity in the intestinal mucosa. ^{32, 33} Curcumin has several anticarcinogenic actions including anti-inflammatory and antioxidant properties. ³⁴ With the high GC mortality-to-incidence ratio and the lack of routine screening methods available for asymptomatic individuals, the management of GC remains a challenge and warrants further investigations to more fully understand the biologic basis of progression and to develop chemopreventive strategies for individuals at increased risk.

MAY2015-05-01 Version 4.0, Amendment 6 May 13, 2019

Population Health Perspective: The Central America Four (CA4) nations (Honduras, El Salvador, Guatemala, and Nicaragua) form the core low/middle income (LMIC) region in the western hemisphere. The CA4 is unified by its geography, history, language, and culture. These countries opened their borders in 2006, and are in transition towards a union of their health systems and infrastructures. A regional approach to cancer control is essential, and cancer capacity-building is imperative. The CA4 population is nearly 35 million, with an estimated immigrant population of 4-5 million, making it unique for cancer control among global LMICs from a U.S. perspective, given the burgeoning U.S. Hispanic population. The Honduras-Puerto Rico partnership in gastric cancer truly provides a unique and powerful platform for chemoprevention and clinical translational studies in Hispanic populations, and the two proposed study sites have characteristics that are appeasing for the current study design, which include:

- Puerto Rico and Central America (Honduras) have a high prevalence of GIM (detected in approximately 20% of asymptomatic patients in the Endoscopy Clinics). However, the sites have different gastric cancer incidence rates,² which will be noted by the use of stratification factors.
- In both Puerto Rico and Honduras, curcumin is not part of the local diet, nor is it readily available. Therefore, dietary curcumin will not be a confounder in the proposed study setting.

[figure not shown]

Figure 1. Meriva reduces gastritis and modulates cytokine responses in murine H. pylori infection.

Findings:

A. Curcumin levels were measured by mass spectrometry in different sites; S, serum; ST, Stomach; SI, small intestine; and C, colon.

B: Quantification of *H. pylori* colonization and histologic gastritis. Veh, vehicle (equivalent to placebo); Mer, Meriva.

C: Representative H&E staining of mouse stomach tissues, showing reduced mucosal thickening and inflammatory cell infiltration with Meriva.

D and **E**: Cytokine levels measured in stomach tissue lysates by the Luminex assay (multiplex bead array). Note in panels D and E, "uninfected" implies never-infected in the mouse model; in human populations, nearly all subjects with IM have had chronic *H. pylori* infection, but may not have measurable active infection in midadulthood. Note that IL-10 is a recognized anti-inflammatory cytokine, demonstrating a potential protective effect from Meriva in panel E.

Supporting Data for Biomarker Endpoints (from mouse models): Findings from recent animal model experiments conducted at Vanderbilt are highlighted in Figure 1 (above).

Panel A: Mice were gavaged with purified curcumin or the equivalent concentration of Meriva® (150 nM) and were sacrificed 1 hour later.

Panels B-E: Young adult mice were continuously fed a diet containing either Vehicle or Meriva® (2% curcumin by weight). Mice were infected with the *H. pylori* SS1 strain. Four months post-inoculation, they were sacrificed and endpoints were measured. (Data provided courtesy of [name], former post-doctoral member of the Vanderbilt Wilson Lab. During this period, [name] was an NIH KO1 Awardee, focused on curcumin and gastric cancer.)

Increasing evidence suggests that tobacco and alcohol use are risk factors in the development of intraepithelial neoplasia and cancer. In addition, tobacco and alcohol use may adversely affect agent intervention, for example by altering the safety profile or metabolism of a drug. Standardized assessments of tobacco and alcohol use during clinical trials will aid in understanding the potential relationship between the use of these products and clinical endpoints or cancer prevention biomarkers. Therefore, NCI, DCP is including assessment of tobacco and alcohol use at baseline and Month 6, to determine the potential impact of tobacco and alcohol use on 1) treatment toxicity and symptom burden, and 2) the efficacy of treatment intervention.

3. SUMMARY OF STUDY PLAN

General Overview: Chronic multifocal atrophic gastritis (MAG) and gastric intestinal metaplasia (GIM) are established precancerous lesions. Participants with MAG, GIM, or both will be identified or confirmed at the baseline upper endoscopy. Willing, eligible trial participants will then be registered and randomized to receive either Meriva® 1000 mg (one 500mg capsule twice per day for a total curcuminoid intake of 200 mg/day) or matching placebo (1 capsule twice per day). A follow-up upper endoscopy will be performed at 6 months (See Schema). We anticipate that the majority of enrolled subjects will have GIM, which confers higher gastric cancer risk. Therefore, baseline histology will be used for stratification.

Screening and Baseline: At both the Puerto Rico and Honduras recruitment sites, potential study participants with a confirmed or suspected diagnosis of gastric MAG and/or GIM will be pre-selected using detailed clinical and research databases that are currently in place and have been demonstrated to be effective for recruitment purposes in other recent studies. Participants who meet the inclusion and exclusion criteria will undergo a comprehensive history and physical examination, alcohol and tobacco use assessments, eligibility/baseline blood testing, *H. pylori* stool antigen testing, research blood collection, and upper endoscopy with biopsies.

Randomization: Eligible participants will be randomized in a 1:1 fashion to 1000 mg Meriva® (one 500mg capsule twice per day, for a total of 200 mg curcuminoids/day) or matching placebo for a 6-month intervention period, using a dynamic allocation procedure called the Pocock-Simon³⁵ that balances marginal distributions of the stratification factors across defined intervention groups and has been shown to be able to accommodate a large number of factors (10-20) without difficulty.³⁶ The randomization will be stratified based on enrolling site (Honduras or Puerto Rico) and baseline gastric mucosal histologic diagnosis (MAG, GIM, or both). The study teams will make weekly phone calls to the participants, and participants will return at 3 months for the assessment of adverse events, blood tests for safety and toxicity, protocol compliance, and concomitant medication usage.

End of Intervention: Participants will return at 6 months for a physical exam; research blood collection, assessment of adverse events, protocol compliance, and concomitant medication

usage, follow-up alcohol and tobacco use assessments, completion of the Was It Worth It (WIWI) questionnaire, and upper endoscopy.

4. PARTICIPANT SELECTION

4.1 Pre-Registration Inclusion Criteria

- 4.1.1 Age ≥21 years. Because no dosing or adverse event data are currently available on the use of Meriva® in younger individuals, and because GIM and MAG are extremely uncommon in children, children are excluded from this study but will be eligible for future pediatric trials.³⁷
- 4.1.2 Ability to understand and the willingness to sign a written informed consent document
- 4.1.3 Willingness to undergo screening tests and procedures
- 4.1.4 Willingness to provide blood and tissue samples for safety/toxicity monitoring and biomarker analyses
- 4.1 5 Willingness to avoid the use of curcumin or any over-the-counter or prescription medications containing curcumin or curcuminoids.

4.2 Pre-Registration Exclusion Criteria

- 4.2.1 History of other malignancy ≤ 2 years prior to the Registration/Randomization evaluation, with the exception of basal cell or squamous cell skin cancer
- 4.2.2 History of colorectal cancer. Exception: Individuals with Stage I or II colorectal cancer who have not received any chemotherapy.
- 4.2.3 Known diagnosis of HIV. Note: An HIV screening test does not have to be performed to evaluate this criterion.
- 4.2.4 History of gastric surgery
- 4.2.5 Receiving any other investigational agents.
- 4.2.6 Use of any anticoagulation medications, such as warfarin or Coumadin
- 4.2.7 Uncontrolled intercurrent illness including, but not limited to, ongoing or active infection, symptomatic congestive heart failure, unstable angina pectoris, cardiac arrhythmia, or psychiatric illness/social situations that would limit compliance with study requirements

4.2.8 Pregnant or breast feeding. Note: Pregnant women are excluded from this study. Because there is an unknown but potential risk for adverse events in nursing infants secondary to treatment of the mother with Meriva®, breastfeeding should be discontinued if the mother is treated with Meriva®.

4.3 Registration/Randomization Inclusion Criteria

- 4.3.1 Histologically-confirmed chronic multifocal atrophic gastritis (MAG) and/or gastric intestinal metaplasia (GIM)
- 4.3.2 *Helicobacter pylori* negative, defined as negative stool antigen testing and negative histological examination.
- 4.3.3 ECOG performance status ≤1 (See Appendix A)
- 4.3.4 Participants must have normal organ and marrow function, defined as lab values (AST, ALT, Alkaline phosphatase, CBC [Platelets, Hemoglobin, WBC], BUN, Total bilirubin, Creatinine) within institutional limits of normal or judged to be not clinically significant by the investigator
- 4.3.5 Not pregnant or breast feeding. Note: The effects of Meriva® on the developing human fetus at the recommended therapeutic dose are unknown. For this reason, individuals of child-bearing potential and men must agree to use adequate contraception (hormonal or barrier method of birth control; abstinence) prior to study entry and for the duration of study participation. Should a woman become pregnant or suspect she is pregnant while participating in this study, she should inform her study physician immediately.

4.4 Registration/Randomization Exclusion Criteria

- 4.4.1 Receiving any other investigational, anticoagulation, and/or chemotherapy agents
- 4.4.2 History of allergic reactions attributed to compounds of similar chemical or biologic composition to Meriva®.

4.5 Inclusion of Women and Minorities

Both men and women and members of all races and ethnic groups are eligible for this trial.

4.6 Recruitment and Retention Plan Summary

Site-specific recruitment, retention, and adherence (RR&A) plans will be submitted by each site as part of the regulatory packet required prior to site activation. In summary, at both the

Puerto Rico and Honduras recruitment sites, potential study participants with a confirmed or suspected diagnosis of gastric MAG and/or GIM will be pre-selected using detailed clinical and research databases that are currently in place and have been demonstrated to be effective for recruitment purposes in other recent studies.

Once on study, study participants will be contacted weekly to encourage and confirm compliance with study procedures. Site teams will document recruitment activities along with reasons for declining participation, not signing the informed consent document, screening failure, and/or discontinuing the study, the latter after registration/randomization. These data will be submitted to DCP, and the recruitment information will be reviewed by the CLO at least quarterly and compared with the plans and deadlines established among the site teams, the CLO, and NCI, DCP.

5. AGENT ADMINISTRATION

Intervention will be administered on an outpatient basis. Reported AEs and potential risks are described in Section 6.2.

5.1 Dose Regimen and Dose Groups

- Meriva®/matching placebo capsules
- 1000 mg (two 500 mg capsules)/day
- Duration 180 days (+/- 14 days)

5.2 Meriva® Administration

- Meriva® will be self-administered.
- Study participants will be dispensed two bottles, each containing 100 capsules (Meriva® or placebo) at baseline and at the 3-month visit. Unused agent will be returned at the 3-month and 6-month visits.
- Participants will self-administer 1 capsule twice daily at approximately the same times each day.
- The dose of 1 capsule twice daily of Meriva® contains 200mg of total curcuminoids within relative standard deviation (RSD) of the given assay for determination.
- Although administration with food is not specified, potential gastrointestinal symptoms may be decreased by consuming the Meriva® with a meal.

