6.3 Availability

Meriva® is an investigational agent supplied to investigators by Thorne Research through a collaborative agreement with NCI, Division of Cancer Prevention (DCP) (see Section 12.7).

At baseline and at the 3-month visit, participants will be provided with two bottles, each containing 100 capsules (500 mg per capsule) of Meriva® or matching placebo.

^{*} Meriva® Investigator's Brochure, 12/06/2016

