7.3 Evaluation During Study Intervention

Participants will be contacted by telephone weekly (+/- 2 days) to assess compliance. Adverse events and concomitant medications will also be assessed and recorded.

At least two weeks prior to the Month 3 visit, the data manager/nurse/pharmacist at the participant's institution must contact the CPN Registration Office at [contact] for code numbers to order additional study product for dispensing to the participant at the Month 3 visit.

At Month 3 (+/- 7 days), participants will return for a study visit, which will include an assessment of vital signs, safety and toxicity blood tests, adverse event and concomitant medications assessment. The study medication diary will be reviewed and collected. Any remaining study agent will be collected. A new study agent supply and medications diaries will be provided.

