7.4 Evaluation at Completion of Study Intervention

The post-intervention evaluation will take place at Month 6 (+/- 14 days), or in the event of early termination. This evaluation will include assessment of adverse events and concomitant medications, follow-up alcohol and tobacco use assessment, WIWI questionnaire, a physical exam and assessment of vital signs, repeat safety/toxicity blood tests, a research blood collection, and repeat EGD with biopsies. Any individuals who discontinue intervention early for any reason will be encouraged to undergo the remaining tests and procedures as scheduled.

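### The Month 3 supply lasts 100 days but the visit windows allow 111 days to the Month 6 biopsy, so a fully adherent participant can be off agent for up to 11 days before the primary IL-1β measurement

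*Combined protocol and SAP*

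**What the plan says.** Section 5.2 sets the dose at one capsule twice daily. On supply it says "Study participants will be dispensed two bottles, each containing 100 capsules", at baseline and again at the 3-month visit; section 6.3 repeats this. Section 7.2.3 describes the first 200 capsules as a supply for 90 days.

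On leftovers, section 5.2 says "Unused agent will be returned at the 3-month and 6-month visits". Section 7.3 describes the visit itself: "At Month 3 (+/- 7 days), participants will return for a study visit". At that visit, "Any remaining study agent will be collected" and then "A new study agent supply and medications diaries will be provided".

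Section 7.4 places the post-intervention evaluation, including the repeat endoscopy with biopsies, at Month 6 with a window of 14 days either side. Section 5.1 gives the course as 180 days with the same tolerance. The schedule in section 7.1 shows dispensing only at registration/randomization and at Month 3. Nothing ties the Month 6 date to the actual Month 3 date, or says that dosing runs up to the endoscopy.

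**The concern.** The supply has a 10-day reserve at nominal timing. The second interval, however, combines two tolerances: Month 3 can be early and Month 6 late. Because unused capsules are collected at Month 3, days saved by an early visit do not carry over. The reserve in the second interval is then only what the new 200 capsules provide.

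Any shortfall falls in the last days before the Month 6 biopsies, which supply the primary endpoint (section 8.1). Only the Meriva arm has an active effect to lose, so days off agent there could pull the comparison toward no difference. Sections 13.6 and 13.8 include everyone with both IL-1β measurements, so these participants count in full. No planned summary reports time from last dose to biopsy by arm.

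**Working it through.** **Inputs.** Capsules per dispensing: 2 × 100 = 200 (5.2, 6.3). Dose: 2 per day (5.2). Month 3 window: ±7 days (7.1, 7.3). Month 6 window: ±14 days (7.1, 7.4). Months are taken as 30 days, in line with the 180-day course in 5.1.

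**The plan's own figure.** For 90 days, 90 × 2 = 180 capsules are needed. With 200 supplied, 20 are spare, or 10 days. The statement in 7.2.3 is correct at nominal timing.

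**Days covered by one dispensing.** 200 / 2 = 100 days.

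**First interval.** The latest Month 3 visit is 90 + 7 = 97 days, needing 97 × 2 = 194 capsules. The supply of 200 is enough, with 6 spare.

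**Second interval.** The longest permitted is (180 + 14) − (90 − 7) = 194 − 83 = 111 days, needing 111 × 2 = 222 capsules. The shortfall is 22 capsules, or 111 − 100 = 11 days.

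**Maximum gap by Month 3 day d:** max(0, 194 − d − 100).

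| Month 3 day | Longest interval to Month 6 | Maximum gap |
|---|---|---|
| 83 | 111 days | 11 days |
| 90 | 104 days | 4 days |
| 94 or later | 100 days or fewer | none |

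**How narrow the condition is.** A gap needs days early at Month 3 plus days late at Month 6 to exceed 10. Of 15 × 29 = 435 permitted day pairs, 66 meet this. The 11-day gap occurs in 1 pair, and the mean over the 66 is 286 / 66 = 4.3 days. These are counts of permitted pairs, not probabilities.

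**Sensitivity to the length of a month (assumption).** With Month 3 on day 91 and Month 6 on day 182 or 183, the maximum gap is 12 or 13 days; with Month 3 on its nominal day it is 5 or 6 days.

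**Course length and compliance in the worst case.** Counting from first dose, days on agent are 83 + 100 = 183, inside the 166 to 194 allowed by 5.1. Capsules taken are 183 × 2 = 366, of 194 × 2 = 388 for a course to day 194, or 94.3%. The 75% rule in 5.7 would not flag this participant. The permitted delay of up to 14 days from registration to first dose (7.2.3) does not change the gap, which depends only on the two visit dates.

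**Power.** The 88% in section 13.4 reproduces: a difference of 7 − 0.5 = 6.5, SD 7.5, 22 per arm and one-sided 0.05 give 88.2% by the noncentral t distribution (42 degrees of freedom). The supply question does not enter that calculation.

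**The case against.** The strongest reply is that this is a corner case of a plan that contains no wrong figure. Nominal timing leaves a 10-day surplus, and the full 11 days needs the earliest Month 3 with the latest Month 6. Even then the participant has 183 days on agent, more than the nominal course, and no section requires a capsule on the days just before the endoscopy. Harm requires IL-1β to rebound within days of stopping, which the documents neither support nor refute. Weekly calls would tell a site that supply was running out, so it could book the endoscopy earlier within its 28-day window. Section 8.3 already lists a supply shortage as a reason for stopping agent. An amendment also needs sponsor and ethics approval (14.3), and regulatory and customs delays have already held up one site by 15 months (13.3).

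Most of this stands, and it limits the weight of the point. It does not remove it. A course of the right total length does not ensure exposure up to the biopsy. Listing a shortage as an off-agent reason records it without preventing it. Calls, diaries and capsule counts may reveal a gap, but nothing obliges a site to act on it and no analysis reports it. The approval burden is a fair reason to prefer the lightest remedy.

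**Conclusion.** The concern holds, as a minor point. As written, the supply and window rules let a fully adherent participant be off agent for up to 11 days immediately before the primary biopsy. The 11 days rests on 30-day months, full adherence, and no re-issue or extra dispensing beyond what is described. The first interval, the course length, compliance status and the 88% power are not affected. The documents give neither the distribution of visit dates nor the rate at which IL-1β returns after stopping, so the frequency of gaps and the size of any dilution cannot be stated. The direction of any bias would be toward no difference.

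**What to change.** In sections 5.2, 6.3 and 7.3, have the site count the Month 3 leftovers and re-issue them with the new supply. With Month 3 on day 83, 200 − 166 = 34 capsules remain; 34 + 200 = 234 covers the 222 needed. Over the whole course, 400 capsules cover 200 days against a latest day of 194. The cost is one more step in agent accountability, where returned quantities are already recorded (6.5).

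If re-issue is not acceptable, there are two alternatives:

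- Dispense a third bottle at Month 3: 300 capsules, 150 days. This costs one more blinded bottle per participant to ship and account for.
- Require the Month 6 endoscopy within 100 days of Month 3 dispensing. This narrows the window: the latest day becomes 183 if Month 3 was on day 83, or 190 if it was on day 90.

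Whichever is chosen, state that dosing continues until the Month 6 endoscopy, and report days from last capsule to endoscopy by arm, using dates already in the diary. The text changes are short and could go into the next amendment.
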